### **7. Reporting Results**

#### **7.1 Individual Results**

No disease screening data will be collected. Patient's changes on clinical tests will be shared with them during testing sessions. These sessions are conducted by licensed Physical Therapists who have training to help persons with stroke interpret clinical examination findings.

#### **7.2 Aggregate Results**

Subjects will not be informed of aggregate findings.

#### **7.3 Professional Reporting**

De-identified, aggregate findings will be published in professional journals and presented at scientific meetings.

## RESEARCH DESIGN AND METHODS

**Description of Home Based Exercise System:** To date, telerehabilitation of the upper extremity has been accomplished by custom built systems designed for rehabilitation. These systems can accommodate a wide variety of impairments but they require extensive assistance for persons with impaired hand function to set up and their cost prohibits broad implementation. Off the shelf gaming systems provide a meaningful alternative for many populations but none of these systems capture finger angles with the accuracy required for rehabilitation. We have developed the New Jersey Institute of Technology – Home Virtual Rehabilitation System (NJIT-HoVRS) to address this limitation and facilitate intensive, hand focused rehabilitation in the home. The system integrates a Leap Motion controller, a passive arm support and a suite of custom designed hand rehabilitation simulations. Novel technologies like the commercially available Leap Motion allow for an affordable and easy-to-use solution to several home based rehabilitation issues that has not existed previously. The Leap Motion provides accurate, camera based measurement of finger angles, allowing for integrated virtual arm and finger activities without an expensive, cumbersome wearable apparatus. If the patient's arm is severely impaired and he/she cannot support the hand against gravity above the Leap Motion Controller (LMC), a spring compensation system (such as the Armon™ Edero or Saebo™ Mobile Arm Support) can be provided to the subject. (Figure 4) This system consists of a forearm orthosis that counter-balances gravity to provide graded support to the arm during activity. These orthoses will be calibrated to provide the least support necessary to complete a simulation within a pre-determined bandwidth of success (usually 70% - 85%. The orthoses will be adjusted (and eventually removed) as patients improve their motor abilities.

[figure not shown]
Using the Unity Game Engine, we have developed a library of interactive games, each designed to focus on training a specific hand movement such as wrist rotation or finger individuation. (see Table 2 below). 3D assets were created using 3DS Max and the interactions were programmed using C#. A comprehensive calibration procedure is used to measure each subject's active range of motion within the LMC visual area and this range is scaled to fit into the video game virtual environment. Motor skills required to accomplish the rehabilitation games are introduced gradually in different game levels. Therefore, as patients progress in game level, they will be training and gaining new motor skills. Therapists can change and save game settings to individualize the games, as ability will vary between patients and the ability level for each patient will vary by day. This configuration and reconfiguration can be performed in the patients' home or remotely by study personnel. Subjects will be able to communicate with study personnel directly via ZOOM, a free, HIPPA-compliant web-conferencing system (Fig 5).

**Treatment Protocol:** Both groups will use the NJIT-HoVRS system and play a series of computer games

**Table 2.** Rehabilitation Games

Description	Enhanced Game	Enhancements	Un-Enhanced Game
Speed Bump Player controls speed of car by opening and closing their hand. Supination / pronation changes lanes. Scoring: Coins collected		Leaderboard Level-scaled graphics Level Scaled scoring Avatar purchases for career scores	
Gesture Flying: Player controls roll, pitch and yaw of the plane flexing and extending wrist Scoring # of Spheres captured		Leaderboard Level-scaled graphics Level Scaled scoring Avatar purchases for career scores	
Maze Runner Direction of runner with horizontal plane reaching. Jumping controlled with hand opening Scoring: # Spheres captured		Leaderboard Level-scaled graphics Level Scaled scoring Avatar purchases for career scores	

targeted to train movement of their shoulder, elbow and fingers. The physical therapist will set up the apparatus in their home and visit them once or twice in the first week to train them how to use the system and how to play the games. After this training period they will then continue to practice in their homes independently with on-line support from the therapist and in-person or on-line assistance from the study-engineer as needed. Both groups will be instructed to perform all three of the simulations assigned to them for at least twenty minutes, daily for twelve weeks.

**Figure 5.** Left: Patient home system setup with the passive arm support, hand tracking device and computer. Right: Patient is able to talk to and see therapist (lower left corner) and while playing games, patient's game screen is shared with therapist at the same time as well.

(career score) on that simulation, and the top ten career scores for the entire program (including other subjects). When users achieve a

The enhanced motivation (EM) group will train using three simulations (See Table 2). These simulations will all provide the user with eight to twelve levels of gradually increasing difficulty and complexity. There is a screen announcing each level change and the graphics for each new level change substantially. Scoring opportunities increase at each new level as well. When a simulation is completed, for the day, a leaderboard displays the user's score for the day, their total points scored for the entire training period

milestone career score (1 million points, two million points, three million points), they will have an opportunity to choose a new avatar for future play. This opportunity is provided at the beginning of gameplay.

The unenhanced control (UC) group will perform the same three simulations. Difficulty will increase utilizing an adaptive control algorithm that increases difficulty based on performance. Difficulty changes are extremely incremental making them imperceptible for most subjects. Graphics and scoring will not change as difficulty level changes. Total score for the day will be displayed after each simulation for the day is completed, but no leaderboard displaying past performances, career scores or the career scores of other subjects will be displayed. UC subjects will use the same avatars for the entire experiment.

**Description of Simulations:** For this study, we have developed a library of 3 task-based simulations that train hand manipulation and arm transport. These simulations include activities such as flexing and extending fingers to move a car, fly a plane with wrist movement and control a man running in a maze using reaching movements. Please see Table 2 for description of each game, scoring, and motivational enhancement techniques used.

## Experimental Design and Training Protocol

### **Aim 1: To test the impact of motivation enhanced, game-based interventions on intrinsic motivation to perform a telerehabilitation exercise program in persons with strokes.**

**Rationale:** Low levels of motivation are cited as the primary barrier to adherence to home based rehabilitation programs. Designing rehabilitation activities that elicit the highest levels of intrinsic motivation is critical to overcoming this barrier and optimizing the effectiveness of home based interventions.

**Hypotheses:** We predict that subjects in the motivation enhanced (ME), game-based intervention group will report higher initial levels of motivation as measured by the Intrinsic Motivation Inventory than those performing un-enhanced control (UC) interventions. We further predict that IMI scores for the ME group will remain higher than those for the UC group.

**Subjects:** This will be a randomized, blinded study. The same subjects will be utilized for all three aims. Upon IRB approval 30 persons with chronic strokes will be recruited from the outpatient rehabilitation department of JFK Medical Center, its hospital based fitness center program for persons with stroke and its stroke support group. **Inclusion criteria** are a) 25-85 years old, b) unilateral stroke, c) score of 24 or greater on the Folstein Mini-Mental Status Exam(52), d) Score of 1 or better on extinction and inattention portion of NIH Stroke Scale (NIHSS)(53), e) Fugl-Meyer (FM) between 30-60/66 (54), f) Score of 1 or better on language portion of NIHSS, g) intact cutaneous sensation (e.g. ability to detect <4.17N stimulation using Semmes-Weinstein nylon filaments(55). **Exclusion criteria are:** Orthopedic issues that would limit the ability to perform regular upper extremity activity. **Randomization:** Because level of impairment may affect (a) compliance with training regime, (b) intrinsic motivation, (c) adherence, and finally (d) measures of effectiveness, it is crucial (especially in a study with limited n) to balance the treatment and control arms. Because simple randomization of subjects to arms may not result in a balanced design, and because the ability to statistically adjust for baseline arm differences in these two characteristics is likely to be limited, we will use the following strategy to ensure arm equivalency. Subjects' initial scores on our measurement of motor control impairment caused by the stroke the (UEFMA) will be dichotomized into low/high. Subjects are then classified into the cell corresponding to their impairment level. Subjects in each cell (n1, n2) are provided random IDs (to prevent an ID by case recruitment association), and an investigator blinded to the randomization process then randomly assigns the first case in each cell to treatment or control arm. Each following subject within the cell is then assigned sequentially to the alternate arm. This is done for all cells to balance the source of variability between arms. **Blinding: Subjects** will be blinded to the purpose of the study and group assignment. They will also be blinded to their previous self-reported scores and their previous performance on objective tests. **Research assistants** performing outcomes measures will be blinded to group assignment and blinded to previous performance on all tests.

**Outcomes Measures:** (See Table 4 for a summary of all measures and Figure 6 for a data collection Schedule). The impact of game mechanics on motivation to perform the simulation that is specifically related to

the experience of using the simulation not the general motivation to improve their hand function or increase their independence, etc. will be measured utilizing the Intrinsic Motivation Inventory (IMI) (58). IMI data will be measured following the first training session (Collection 2) to measure the subjects' initial reaction to the system and simulations as well as after the twelfth session (Collection 3) and after the final training session (Collection 4) to chart subjects' responses to repeated use.

*Statistical Analysis:* (See Table 5 for a summary of all planned comparisons) Our primary outcome measures will compare differences in IMI scores after the initial exposure to the training program. Data will be evaluated for normality and transformed if necessary for evaluation. Baseline group equivalence will be evaluated via t-test. The within-and-between group interaction will be examined to evaluate differences in change between groups.

**Aim 2: To test the impact of intrinsic motivation on adherence to a telerehabilitation exercise program in persons with strokes.**

**Table 4** Outcome measures

Motivation Measure	
Intrinsic Motivation Inventory	Measurement of emotional response to an activity.
Adherence Measures	
Number of interventions days	Recorded by system
Total intervention time	Recorded by system
Average intervention day time	Recorded by system
Clinical Measures	
Upper Extremity Fugl-Meyer Assessment (66)	A 33 item battery which evaluates reflexes, movement patterns in and out of synergy, grasp, and coordination (impairment level)
Action Research Arm Test (62)	19 item battery which tests the ability to handle items of different size, shape and weight (activity level)
Box and Blocks Test (67)	Standardized dexterity test with well-established benchmarks for persons with CVA and age-matched healthy populations
Quality of Life Measure	
Stroke Impact Scale (69)	Patient reported assessment of multiple activity and participation level domains post stroke including hand function, activities of daily living and social participation.
Kinematic/Kinetic Measures	
Hand opening/closing range of motion	Sum of maximum angular excursions of the paretic metacarpophalangeal (MCP), proximal inter-phalangeal (PIP) and distal inter-phalangeal joints (DIP) joints.
Hand opening velocity	Peak angular velocity during hand opening
Hand trace RMSE	Ability to control hand opening as subject moves a cursor tracking a sine wave. Reported as root mean square error (RMSE) comparing target position and cursor position.
Wrist Trace RMSE	Ability to control wrist flexion and extension as subject moves a cursor tracking a sine wave. Reported as root mean square error (RMSE) comparing target position and cursor position.
Horizontal shoulder and elbow trace RMSE	Ability to control shoulder and elbow as subject moves a cursor tracking a sine wave. Reported as root mean square error (RMSE) comparing target position and cursor position.

*Rationale:* Very few rehabilitation studies examine the interaction between motivation and adherence quantitatively. Utilizing knowledge of this interaction to inform design of rehabilitation simulations should advance the field of home based rehabilitation substantially.

*Hypothesis:* We predict that intrinsic motivation related to game play will predict adherence more effectively than patient readiness alone.

*Subjects:* The same subjects will be utilized for all three aims.

*Outcome measurements:* will include number of sessions as well as total intervention time and average session time. Time signatures from the telerehabilitation system will be used to overcome overestimation effects associated with patient self-reports of actual exercise time (59).

In an attempt to expand our understanding of the interaction between motivation (as measured by the IMI) and adherence to the autonomous home rehabilitation program, we will perform an in depth qualitative analysis focusing on subjects' unique perceptions and understandings of their participation in the proposed rehabilitation program. Using a Grounded Theory approach (60, 61), data collection and analysis will follow

these steps: 1) A trained interviewer will ask open-ended questions in telephone interviews, allowing participants to reflect on and describe their experiences. 2) Investigators will read participants' narratives to develop a general sense of the subjects' experiences and attitudes toward the rehabilitation program. 3) Investigators will identify emerging narrative themes in participants' experiences and attitudes toward the program. 4) Finally, an iterative coding process will be used to refine initial findings and synthesize these themes.

*Statistical Analysis:* (See Table 5 for a summary of all planned comparisons.) Linear regression will be used to evaluate the effects of IMI (From Data Collection 1) on total time (Collected during training sessions).

**Aim 3: To test the impact of motivation enhanced, game-based interventions on the effectiveness of a telerehabilitation exercise program in persons with strokes.**

*Rationale:* Studies of clinic based interventions targeting hand function in persons with stroke have produced measurable changes in hand function that do not substantially reduce hand related disability. Study of a long term, home based program emphasizing adherence will inform the development of sustainable alternatives to costly clinic based interventions that fall short of the ultimate goal of rehabilitation.

*Hypothesis:* We predict that subjects in the ME group will demonstrate larger improvements in hand function as measured by the Action Research Arm Test (ARAT) than those performing UC interventions. We further predict that subjects in the ME group will demonstrate larger reductions in impairment and larger improvements in measures of motor control and quality of life than UC group subjects.

*Subjects:* The same subjects will be utilized for Aims 1-3.

*Outcome Measures:* (Please see Table 4 for the full listing and description of the proposed clinical and quality of life measures.) A trained RA, blinded to group assignment will collect all outcome measures described in Table 4 immediately prior to training, immediately after training and 3 months after training (Data Collections 1 and 2). The RA will be blinded to previous test scores during post testing and retention testing.

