## Home Based Virtual Rehabilitation for upper extremity

**Title of Project:**

**Principal Investigator:**

**[name] PT PhD**

**Funding Source(s):**

**NIDILRR #90RE5021-01-00**

**NIH NICHD #1R15HD095403-01A1**

### 1. Purpose/Specific Aims

The overarching aim of this study is to provide a mechanism for patients to engage in progressive motor practice for a meaningful time period. We aim to improve on the positive outcomes found in our work on patients in the chronic phase and the pilot work being done on patients in the acute in-patient phase post stroke to determine whether we can further improve functional recovery using a home based system.

Aim 1: Evaluate compliance with Home-Based Virtually Simulated hand/arm gaming activities and two computer game groups, one with motivation enhanced (ME) simulations and one with non-enhanced (MnE) versions, as compared to compliance with Standard hand/arm home Exercises (HBSE). Hypothesis: Participants in the ME and MnE group will show significant compliance as compared to the control group (HBSE) and the ME group will be superior to the MnE group.

Primary Outcome Measures: For the HBVS group, 1) time on task will be measured by the daily computer file time stamp and 2) amount of moving time will be measured by the actual movement time recorded by the games. For the computer games groups 1) time on task will be measured by recording start and stop time of practice in a notebook and 2) amount of moving time will be measured by commercially available activity monitors.

Aim 2: Evaluate the effectiveness of home-based virtually simulated hand/arm gaming activities (HBVS) for individuals with stroke as compared to a program of standard hand/arm home exercises (HBSE). Hypothesis: Participants completing HBVS training will exhibit significantly improved clinical, kinematic and neurophysiological outcomes as compared to the control group (HBSE).

Primary Outcome Measures for Aim 2: Wolf Motor Function Test, Upper Extremity Fugl-Meyer Assessment of Sensorimotor Recovery after Stroke, Action Research Arm Test, Perception of System Questionnaire, the Stroke Impact Scale, Kinematics, Cortical mapping.

Aim 3: Evaluate the impact of the motivation enhancements designed into computer games to provide a more enjoyable training experience. Hypothesis: Enjoyment of the games will be a more valid predictor of compliance than personal factors.

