### ***3.4 Subject Selection and Enrollment Considerations***

#### ***3.5.1 Inclusion Criteria***

- 1) healthy persons between the ages of 20 and 90
- 2) persons six weeks post stroke between the ages of 20 and 90
- 2) person with enough shoulder, elbow, wrist, and hand movement to actively interact with the video games

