#### ***3.5.2 Exclusion Criteria***

- 1) person with severe arm weakness and cannot move the arm enough to interact with the video games
- 2) person with severe increase in tone of their weak arm
- 3) person with difficulty following instructions or paying attention to computer video games for at least ten minutes,
- 4) person with visual problems that make it difficult for them to interact with an entire computer screen

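### The protocol and SAP define different, non-nested study populations, and neither says which list governs or which applies to the standard-exercise arm

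*SAP*

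**What the plan says.** **SAP, Aim 1, Subjects.** "Upon IRB approval 30 persons with chronic strokes will be recruited", from one medical centre's outpatient, fitness and support-group programmes. The age limit is "25-85 years old" and the motor limit is "Fugl-Meyer (FM) between 30-60/66". Everyone needs a Mini-Mental score of 24 or more. There are further limits on laterality, neglect, language and skin sensation, and an orthopaedic exclusion. The two SAP arms both play games on the home system. Allocation is within low and high UEFMA cells: the first case is random and later cases alternate.

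**Protocol, sections 3.5.1 and 3.5.2.** The list includes "healthy persons between the ages of 20 and 90" and "persons six weeks post stroke between the ages of 20 and 90". The motor requirement is "person with enough shoulder, elbow, wrist, and hand movement to actively interact with the video games", and the matching exclusion is "person with severe arm weakness and cannot move the arm enough to interact with the video games". Neither carries a score. Severe tone, poor attention to the games and visual problems are also excluded. Section 3.5.4 calls for a Mini-Mental only when dementia is suspected at consent, with no cut-off. Section 3 allocates by computer-generated random numbers and names no strata.

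**Protocol, section 1, Aim 1.** The hypothesis involves a third arm: "Participants in the ME and MnE group will show significant compliance as compared to the control group (HBSE"). The SAP has no such arm.

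**The concern.** A site cannot follow both lists. A person eight weeks after stroke, or aged 22, can be eligible under one document and not under the other. The choice of list decides who is enrolled and to whom the results apply.

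It also bears on which contrasts are randomised. HBSE appears only in the protocol, so only the protocol's list covers it. The game arms appear in both documents, under two lists, two recruitment routes and two allocation methods. If staff filled the game arms from the SAP and HBSE from the protocol, the protocol's Aim 1 contrast would compare different kinds of patient as well as different treatments.

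The SAP explains why that would matter: it says impairment may affect compliance, motivation, adherence and effectiveness, and it treats balance on impairment as crucial. Protocol section 3.3 says screening will aim for homogeneous impairment, yet the protocol's criteria contain no impairment score.

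**Working it through.** The plan gives no figure on this point to reproduce. The sample size in protocol section 3.3 has no term for case mix. The check is a comparison of the lists, then of the arms that each covers.

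**Step 1: the two lists.**

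| Item | Protocol 3.5.1, 3.5.2, 3.5.4 | SAP Aim 1, Subjects |
|---|---|---|
| Stroke phase | six weeks, read here as a minimum; no chronic requirement | chronic |
| Laterality | not stated | unilateral |
| Age | 20 to 90 | 25 to 85 |
| Motor ability | able to play the games; no score | Fugl-Meyer 30 to 60 of 66 |
| Cognition | attention and instruction-following exclusion for all; Mini-Mental only on suspicion | Mini-Mental at least 24 for all |
| Neglect, language | no scored limit; screen-vision and attention items overlap in part | NIHSS item limits |
| Sensation | not stated | filament threshold |
| Orthopaedic limits | not stated | excluded |
| Severe tone | excluded | no direct counterpart |
| Visual problems | excluded | no direct counterpart |
| Healthy persons | listed | not listed |

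**Step 2: nesting.** The protocol is wider on age (ages 20 to 24 and 86 to 90 qualify only there), stroke phase and motor score. The SAP is wider on tone and vision, where it states no exclusion. Neither list is a subset of the other, so following the stricter-looking one does not satisfy both.

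**Step 3: which arms each list covers.**
- Protocol list: ME, MnE and HBSE.
- SAP list: the enhanced and unenhanced game arms only.
- All arms under the protocol list: the ME and MnE versus HBSE contrast is randomised.
- Both game arms under the SAP list: the contrast between them comes from one population.
- Game arms under the SAP and HBSE under the protocol: the contrast is not randomised. The SAP's UEFMA cells cannot repair it, because they balance only the two game arms.

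**Step 4: what the visible models contain.** The ANOVA in protocol section 5 has Therapy Type and Test. SAP Aim 1 has a baseline t-test and a group-by-time interaction. SAP Aim 2 regresses total time on IMI. None names baseline UEFMA or time since stroke. SAP Table 5 and an Aim 3 analysis are not in the text available, so this covers only the models that can be seen.

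**Step 5: illustration for the third case only.** Assume no treatment effect and a case-mix difference of s SD between two arms. The assumed range is 0.1 to 0.5; the documents give no value. The two-sided 5% t-test has noncentrality s / √(1/n₁ + 1/n₂).
- 25 v 25 (section 3.3 size): √(1/25 + 1/25) = 0.283. For s = 0.3, noncentrality is 0.3 / 0.283 = 1.06 on 48 df. False rejection is 6%, 18% and 41% for s = 0.1, 0.3 and 0.5.
- 30 v 15 (HBSE at the protocol's 30; one game arm at half of the SAP's 30): √(1/30 + 1/15) = 0.316. For s = 0.3, noncentrality is 0.3 / 0.316 = 0.95 on 43 df. False rejection is 6%, 15% and 34%.

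These figures show sensitivity to an assumption and do not estimate bias in this trial.

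**The case against.** The strongest reply is that each document, followed on its own, assigns all its arms from a single list, and no passage says that arms are filled from different lists. That stands. A reader might infer from the mismatch that the arms are not comparable; the documents do not support it.

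The SAP may also describe a separate sub-study. It has its own two arms, 30 subjects, recruitment source and primary outcome (IMI), and the protocol names two funding sources. On that reading neither document's randomised contrast is biased, and one clarifying sentence would settle the matter. This is plausible, but neither document says it.

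Impairment is not ignored, since the SAP balances its arms on UEFMA. The SAP also doubts that adjustment can do much in a small sample. That doubt is a fair caution against relying on covariates to fix imbalance. It is weaker against adding one covariate that already defines the allocation cells.

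Finally, the lists overlap more than a count of differences suggests: the protocol's attention and vision exclusions do part of the work of the SAP's cognition and neglect limits.

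**Conclusion.** The inconsistency is real and should be resolved. The two documents define incompatible, non-nested populations, neither says which governs, and only the protocol's list covers HBSE.

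The certain consequence is an undefined target population. Confounding of the game arms versus HBSE contrast by stroke phase and impairment is conditional on the arms being filled under different lists. Its size cannot be taken from the documents, and any SD figure rests on assumed inputs.

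Two other strong readings also go too far. A reader might infer that no planned analysis deals with impairment, but the SAP allocates on UEFMA and part of its analysis plan cannot be seen. A reader might infer that healthy persons will be randomised; the protocol lists them as eligible without saying what role they have. The conclusion assumes that six weeks is a minimum and that the protocol's MnE arm and the SAP's unenhanced control are the same intervention.

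**What to change.** 1. Put one eligibility list in both documents for every arm that is compared, leaving the clinical limits to the sponsor. Alternatively, state which list applies to which cohort and that contrasts across lists are not randomised comparisons.
2. State the role of healthy persons, and whether the SAP is a sub-study or the analysis plan for the whole protocol.
3. Include baseline UEFMA as a covariate in the WMFT, ARAT and adherence models. It is already measured before training and forms the SAP's allocation cells.
4. If people from six weeks after stroke remain eligible, add time since stroke to the same models.

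The cost is a wording change plus one or two degrees of freedom in a small sample, using baseline data obtainable at screening. Covariates cannot rescue arms that do not overlap in stroke phase, because adjustment would then be extrapolation. Item 1 is therefore the essential change, and items 3 and 4 do not replace it.

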## **3. Research Design and Methods**

This study will be a single blind randomized controlled trial. Subjects will be blinded to the purpose of the study. All outcome measures will be performed by a therapist blinded to group assignment. A controlled trial will be utilized to determine the additive effect of presenting rehabilitation activities in a virtual environment as compared to standard upper extremity exercise. We will randomize subjects to treatment and control groups using a computerized random number generator.

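### Allocation alternates after the first case in each UEFMA cell: in enrolment order, 28 of 30 assignments are predictable, and no concealment is described

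*SAP*

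**What the plan says.** The SAP (Aim 1, Subjects, Randomization) plans for 30 people: "Upon IRB approval 30 persons with chronic strokes will be recruited from the outpatient rehabilitation department of JFK Medical Center". Baseline UEFMA is dichotomised into low and high, which gives two cells. Within each cell the steps are:

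- Subjects "are provided random IDs (to prevent an ID by case recruitment association").
- Then "an investigator blinded to the randomization process then randomly assigns the first case in each cell to treatment or control arm".
- Then "Each following subject within the cell is then assigned sequentially to the alternate arm".

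The stated aim is balance between the arms in a small study. Subjects and outcome assessors are to be blinded. Nothing is said about blinding the staff who enrol or treat.

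The SAP's Treatment Protocol shows that treating staff learn the arm. "The physical therapist will set up the apparatus in their home and visit them once or twice in the first week", and the Figure 5 caption says that during remote contact the patient's "game screen is shared with therapist at the same time as well". The two versions look different: in the unenhanced arm, "no leaderboard displaying past performances, career scores or the career scores of other subjects will be displayed".

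The Protocol (section 3) says only this: "We will randomize subjects to treatment and control groups using a computerized random number generator". It mentions no strata, no alternation and no concealment.

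**The concern.** Stratifying by UEFMA is sensible. The weakness is the rule within each stratum, where one random draw fixes every later assignment. Once the first arm in a cell is known, the rest of that cell's sequence is known too.

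That matters if anyone who influences enrolment, or its timing, can work out the next arm. They need two facts: the last arm used in the cell, which treating staff can see, and the candidate's UEFMA level. A Fugl-Meyer score of 30 to 60 is an inclusion criterion, so whoever screens may well have the second fact before assignment. Blinding subjects and assessors does not close this route, because selection happens before allocation.

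The same subjects serve all three aims, so the between-arm comparisons of IMI (Aim 1) and of ARAT and the other outcomes (Aim 3) rest on this allocation. Analysis could not easily repair selection on motivation: under Aim 1 the first IMI is taken after the first training session, and the SAP itself expects only limited ability to adjust for baseline differences.

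**Working it through.** The plan gives no predictability figure to reproduce, so this is a count followed by a sensitivity calculation.

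**Inputs from the SAP (Aim 1).** N = 30; two UEFMA cells; one random assignment per cell; alternation afterwards.

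**Assignments fixed in advance, enrolment order.** Fixed = N − number of cells = 30 − 2 = 28, and 28/30 = 93%. This holds for any split with both cells non-empty. Only 2² = 4 sequences are possible.

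**Correct guesses under alternation.** The 28 fixed assignments are guessed with certainty and the two first cases at 0.5: (28 + 2 × 0.5)/30 = 29/30 = 96.7%.

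**Correct guesses under random blocks of 2 and 4 within cell.** The guesser picks the lagging arm in the cell; ties count 0.5. Simulation (20,000 trials) gives 70.6% for cells of 15/15 and 71.7% for 14/16, 12/18 and 10/20.

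**Known fixed block of 4, for comparison.** In a full block the fourth assignment is always determined, and the third is determined with probability 1/3: 1 + 1/3 = 4/3 per block. A part-block of three adds 1/3.

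- Cells 15/15: 2 × (3 × 4/3 + 1/3)/30 = 8.67/30 = 28.9%.
- Cells 12/18: (3 × 4/3 + 4 × 4/3)/30 = 9.33/30 = 31.1%. Cells 10/20 give the same.

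**What steering could do.** Assumption, not from the documents: when staff have a basis for a guess, they shift the enrolled patient's expected outcome by d SD towards the predicted arm, with d from 0.1 to 0.3. There is no true effect, the SD is 1, and the test is a two-sample t-test with 15 per arm.

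With guess rate g, correct minus wrong guesses make up 2g − 1 of assignments, so the expected bias is 2d(2g − 1).

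- Alternation: 2d × (2 × 0.967 − 1) = 1.87d.
- Blocks of 2 and 4: 2d × (2 × 0.706 − 1) = 0.82d.

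Simulation (30,000 trials) agrees to within rounding:

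| d (SD) | Alternation: bias (SD) | Alternation: type I error | Blocks 2/4: bias (SD) | Blocks 2/4: type I error |
|---|---|---|---|---|
| 0 | 0 | 4.9% | 0 | 4.9% |
| 0.1 | 0.19 | 7.9% | 0.08 | 5.6% |
| 0.2 | 0.37 | 16.7% | 0.17 | 7.1% |
| 0.3 | 0.56 | 31.6% | 0.25 | 9.3% |

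**Other readings of the rule.**

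- If each cell were filled first and then alternated in random-ID order, enrolment order would fix no assignment. Balance alone would allow about 18.5 of 30 correct guesses (62%).
- The SAP speaks of two characteristics but names only UEFMA. If a second factor made four cells, 30 − 4 = 26 of 30 (87%) would be fixed.

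**The case against.** The strongest reply is that the SAP may not intend enrolment order. Random IDs are issued within cells just before the first assignment, and that step would do nothing for allocation if subjects were simply taken as they came. No UEFMA cut-point is given either, and a sample-based split would need all the scores first. Both fit a design in which cells are filled and then assigned. This makes the text ambiguous, but the SAP never says that assignment waits until a cell is full, and under rolling recruitment a random ID hides nothing. The 28 of 30 figure is therefore conditional on enrolment order.

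Second, 97% assumes a guesser who knows both the last arm and the candidate's cell. Neither document says that the therapist enrols subjects, and a blinded assistant collects the pre-training measures. Someone who knows the last arms but not the candidate's cell would be right only about three quarters of the time. That is fair, but the Fugl-Meyer inclusion range puts the score within reach of the person screening.

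Third, the bias figures rest on an assumed steering effect, and it is not obvious how staff would foresee a reaction to a game not yet played. This stands: the table shows exposure, not a forecast.

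Fourth, two side points are weak. The investigator described as blinded to the process is named only for the first case; no one is named for the later ones. A random number generator could also supply the IDs and the first draws, so the Protocol is incomplete on this rather than plainly contradictory.

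Finally, part of the SAP was not available, so the absence of concealment is a finding about the available text only.

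**Conclusion.** The concern holds and should be fixed before allocation begins. The plan states an allocation rule under which, in enrolment order, 93% of assignments are fixed by the one before, and the available text offers no safeguard. The count needs only two non-empty cells and assignment in enrolment order. The 97% guess rate also needs someone who knows the last arm and the candidate's UEFMA level. The bias of 0.19 to 0.56 SD and type I error of 8% to 32% further depend on an assumed steering of 0.1 to 0.3 SD, which nothing in the documents supports or rules out. The case for change does not rest on that assumption: the balance the SAP wants can be had with much less predictability.

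**What to change.** Replace alternation in the SAP with a computer-generated list, stratified by a pre-specified UEFMA cut-point, with undisclosed block sizes that vary at random (for example 2 and 4). Give the list to an existing team member who has no part in enrolment, set-up or testing. That person releases one assignment at a time, after eligibility and baseline UEFMA have been recorded. State the order of assignment and the role that makes it, and reconcile the text with section 3 of the Protocol. Include the UEFMA stratum in the between-arm models, since allocation is stratified on it.

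The cost is a generated list, one named role and some SAP wording, with no extra procedure for subjects. Balance loosens slightly: the maximum imbalance becomes 2 per stratum and 4 overall, against 1 and 2 under alternation. Some predictability remains, at 71–72% correct guesses for someone who tracks the lagging arm, against 97% under alternation.
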